Data Disclosure

Will the data be disclosed to anyone who is not listed under Personnel?

Project collaborators on the BCFG Scientific Team at other institutions will be given access to the data via access to the LDI HSRDC (see subject confidentiality for details). The list of such collaborators will be uploaded as a separate attachment in a protocol modification before any data is shared with them.

Collaborators will be required to sign a data use agreement prior to receiving access to the data.

Data Protection*

- x **Name**
- x **Street address, city, county, precinct, zip code, and equivalent geocodes**
All elements of dates (except year) for dates directly related to an individual and all ages over 89
- x **Telephone and fax number**
Electronic mail addresses
Social security numbers
- x **Medical record numbers**
Health plan ID numbers
Account numbers
Certificate/license numbers
Vehicle identifiers and serial numbers, including license plate numbers
Device identifiers/serial numbers
Web addresses (URLs)
Internet IP addresses
Biometric identifiers, incl. finger and voice prints
Full face photographic images and any comparable images
Any other unique identifying number, characteristic, or code
None

Does your research request both a waiver of HIPAA authorization for collection of patient information and involve providing Protected Health Information ("PHI") that is classified as a "limited data set" (city/town/state/zip code, dates except year, ages less than 90 or aggregate report for over 90) to a recipient outside of the University of Pennsylvania covered entity?

Yes

The following documents are currently attached to this item:

There are no documents attached for this item.

Tissue Specimens Obtained as Part of Research*

Are Tissue Specimens being obtained for research?

No

Tissue Specimens - Collected during regular care*

Will tissue specimens be collected during regulator clinical care (for treatment or diagnosis)?

No

Tissue Specimens - otherwise discarded*

Would specimens otherwise be discarded?

No

Tissue Specimens - publicly available*

Will tissue specimens be publicly available?

No

Tissue Specimens - Collected as part of research protocol*

Will tissue specimens be collected as part of the research protocol?

No

Tissue Specimens - Banking of blood, tissue etc. for future use*

Does research involve banking of blood, tissue, etc. for future use?

No

Genetic testing

If genetic testing is involved, describe the nature of the tests, including if the testing is predictive or exploratory in nature. If predictive, please describe plan for disclosing results to subjects and provision of genetic counseling. Describe how subject confidentiality will be protected Note: If no genetic testing is to be obtained, write: "Not applicable."

Not applicable

Consent

1. Consent Process

Overview

We are requesting a waiver of informed consent (see below).

Children and Adolescents

Not applicable

Adult Subjects Not Competent to Give Consent

Not applicable

2. Waiver of Consent

Waiver or Alteration of Informed Consent*

Waiver or alteration of required elements of consent

Minimal Risk*

Participation in this study does not substantially differ from what patients typically experience in the way of appointment-related communications from their health system (Trial A) or customers typically experience when they receive messages from their pharmacy (Trial B). For Trial A, Penn Medicine and Geisinger patients will receive text messages prior to their scheduled appointments about receiving a flu vaccination. As part of their normal operations, Penn Medicine and Geisinger Health send patients appointment reminders prior to their scheduled appointments and encourage their patients to get the flu vaccination. This project has received approval from the Penn Medicine privacy office, Information systems committee, and Penn medicine executive leadership. The study has been socialized with the Geisinger Health Immunization Steering Committee, which has representatives from Marketing, the Care Gaps team, infectious disease, Pharmacy, and the Geisinger Health system CMO, and there were no concerns. For Trial B, Walmart pharmacy customers will be included if they already receive pharmacy text messages from Walmart.

Impact on Subject Rights and Welfare*

Subjects' rights and welfare will not be adversely affected by this waiver. Subjects are free to seek or forego flu vaccination at any time during or after the study, at their appointment, pharmacy, or any other vaccination provider.

Waiver Essential to Research*

It is not feasible to obtain informed consent from subjects in this study. It would be logistically difficult to obtain informed consent from subjects before texting them intervention messages. Furthermore, for many patients or customers, introducing the idea of research into their relationship with their health care provider or pharmacy would be the most negative part of the entire experience in the study. Patients expect to receive communications from their provider about their appointments and from their pharmacy about flu shots but do not expect to be communicating about research. Bringing up research could also cause the surprised patients to refuse -- possibly to the detriment of their health -- flu vaccination options that they would otherwise have accepted.

Additional Information to Subjects

Participants will not receive additional information about the research.

Written Statement of Research*

No

If no written statement will be provided, please provide justification**The following documents are currently attached to this item:**

There are no documents attached for this item.

Risk / Benefit**Potential Study Risks**

This study poses minimal risks to health or well being. Flu shots are sometimes accompanied by side effects, but the subjects in this study would have access to flu shots in the absence of the intervention, and the benefits of becoming inoculated substantially outweigh the risks.

Potential Study Benefits

The current research is aimed at finding better methods for encouraging individuals to receive vaccinations to improve their health. We expect that our results will provide insights that health care providers can use to encourage vaccinations. In addition, participants may be more likely to receive a flu shot, which will make them less susceptible to the flu. See <https://www.cdc.gov/flu/prevent/vaccine-benefits.htm> for the benefits of the flu shot.

Alternatives to Participation (optional)**Data and Safety Monitoring**

The PIs will be responsible for monitoring the study. Data will only be accessible on password- and firewall-protected servers to ensure that only the researchers have access to it.

The following documents are currently attached to this item:

There are no documents attached for this item.

Risk / Benefit Assessment

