they have consented to receive text messages about their prescriptions and have received a flu shot from Walmart in the past. Intervention content will be delivered via text message to Walmart pharmacy customers at the start of the flu season. Between Trial A and Trial B, we plan to include at least 40 different experimental conditions designed by the Behavior Change for Good Scientific Team (including researchers at Penn and other institutions), by Geisinger employees, and by Walmart employees. Interventions may vary the content and timing of text messages (including whether messages are interactive or provide links to surveys and videos). Interventions may also include incentives for behaviors of interest (e.g., receiving the flu shot or completing a survey), the details of which would be described in the text messages themselves. Details of each experimental condition have been included as a separate attachment as a modification to this protocol. Text messages may include first name, appointment date and time, provider name, and practice/pharmacy locations. This is in line with the standard appointment reminders that Penn Medicine patients receive, which includes first name, appointment date and time, and department information. Specifically, the Penn Medicine reminders say "PENNMED: (First Name) has an appt (APPT Date /Time)@(SMS Department Abbreviation). To confirm txt YES. To decline txt NO. Txt Help 4help." Any additional information that we include in text messages to participants beyond that does not include HIPAA information. All messages will be reviewed and approved by our partners before being launched.

Group Modifications

Describe necessary changes that will or have been made to the study instruments for different groups. The content and timing of text messages and incentives will vary according to which intervention participants are assigned. Specific messages and incentive information has been added as a modification.

Method for Assigning Subjects to Groups

Describe how subjects will be randomized to groups.

In Trial A, patients will be randomly assigned to experimental conditions using stratification that accounts for demographics (e.g., age), and recruitment site. Trial B will also randomly assign participants to experimental conditions, and may also use stratification that accounts for demographics (e.g., age).

Administration of Surveys and/or Process

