For Trial A, Penn Medicine and Geisinger Health patients with scheduled primary care appointments during the Fall 2020 flu season who receive SMS reminders about their appointments from their health system will be randomly assigned to receive one of our study's SMS interventions. Text messages will be sent up to four days prior to patients scheduled primary care appointments. These messages will be sent via Penn Medicine's WayToHealth Platform. All messages (including participants' responses to messages) will be stored on the HIPAA-compliant WayToHealth platform. Patient phone numbers from their Penn Medicine and Geisinger records will be shared with WayToHealth to deliver the text messages. Some messages will be personalized based on patient information (e.g., first name) and Penn Medicine/Geisinger appointment information (e.g., practice name). All identifiable patient information will be removed from the dataset that is shared with researchers for analysis. For Trial B, Walmart pharmacy customers who have consented to receive SMS messages about their prescriptions and have received a flu shot from Walmart in the past will receive messages at the start of the flu season. Messages may be personalized based on customer information (e.g., first name) and/or Walmart pharmacy information (e.g., pharmacy location). These messages will be sent via Walmart pharmacy's text messaging platform. All identifiable customer information will be removed from the dataset that is

shared with researchers for analysis.

Data Management

Describe how and who manages confidential data, including how and where it will be stored and analyzed. For instance, describe if paper or electronic report forms will be used, how corrections to the report form will be made, how data will be entered into any database, and the person(s) responsible for creating and maintaining the research database. Describe the use of pseudonyms, code numbers and how listing of such identifiers will be kept separate from the research data.

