For Trial A, intervention content will be delivered to participants via text messages from the WayToHealth platform. Penn Medicine and Geisinger will provide the patient data and appointment data needed for WayToHealth to deliver the interventions. This may include a unique identifier, medical record number, first and last name, address, appointment date, appointment time, appointment type, practice and physician information, patient town and zip code, date of birth, gender, phone number(s), documented allergy to the flu shot, and documentation of flu shot receipt for the 2020 flu season. Penn Medicine and Geisinger will also indicate which phone numbers have opted out of receiving text message reminders. WayToHealth will receive these data from Penn Medicine via a secure data feed and from Geisinger via a secure upload. There will be data use agreements in place governing the data sharing with WayToHealth and Wharton as required. The Penn Medicine Academic Computing Services (PMACS) will be the hub for the hardware and database infrastructure that will support the project and is where the WayToHealth web portal is based. The PMACS is a joint effort of the University of Pennsylvania's Abramson Cancer Center, the Cardiovascular Institute, the Department of Pathology, and the Leonard Davis Institute. The PMACS provides a secure computing environment for a large volume of highly sensitive data, including clinical, genetic, socioeconomic, and financial information. Among the IT projects currently managed by PMACS are: (1) the capture and organization of complex, longitudinal clinical data via web and clinical applications portals from cancer patients enrolled in clinical trials; (2) the integration of genetic array databases and clinical data obtained from patients with cardiovascular disease; (3) computational biology and cytometry database management and analyses; (4) economic and health policy research using Medicare claims from over 40 million Medicare beneficiaries. PMACS requires all users of data or applications on PMACS servers to complete a PMACS-hosted cybersecurity awareness course annually, which stresses federal data security policies under data use agreements with the university. After the end of the intervention, patient and intervention data will be transferred from WayToHealth, Penn Medicine, and Geisinger to the Leonard Davis Institute's Health Services Research Data Center (HSRDC), which is maintained at a high security level in accordance with federal regulations (e.g., HIPAA) governing secure computer systems. This will include all data used for study implementation (i.e., the full list included above), as well as additional data to be used in analysis. The additional data may include patient diagnosis, procedures, and prescription information from the previous 5 years, marital status, and whether they have children, race/ethnicity, Charlson Comorbidity score, insurance type, a record of previous flu vaccinations from the previous 5 years, a record of all doctor visits in the past year, appointment arrival time, preferred pharmacy, number of emergency contacts and relation to emergency contacts, patient body mass index, smoking status, record of prior positive test for the flu, and primary care physician (PCP) specialty. Storage and analysis protocols for the data on the LDI HSRDC will be included in the data use agreement with Geisinger and Walmart. All identifiable data will be removed from this list as soon as possible, and will not be used for analysis. The Geisinger investigators will have access to data on (1) any intervention(s) they design, and (2) intervention data for Geisinger patients across all interventions for the purpose of running internal analyses through the HSRDC. They will handle all data in accordance with Geisinger and IRB policies. For Trial B, Walmart pharmacy will deliver the interventions directly to eligible Walmart pharmacy customers via their own text messaging platform. At the end of the intervention, Walmart pharmacy will transfer intervention data (e.g., to which intervention each customer was assigned, text messages sent and received) along with customer pharmacy and medical data (e.g., whether they received a flu shot, previous medical diagnoses) and customer demographic data (e.g., age, gender) to the HSRDC for analysis. Identifiable data will not be shared. For both Trial A and Trial B, collaborators at Penn and other institutions will access and analyze the non-identifiable data on participants assigned to the interventions they designed through the HSRDC. The server does not allow data to be copied or moved off of the server. Access will only be granted to investigators at other institutions after a data use agreement with Penn has been executed.

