Trial A: Penn Medicine and Geisinger patients will be included if they: - Have a cell phone number recorded in a Penn Medicine or Geisinger database - Have a new or routine primary care appointment during the Fall 2020 flu season (not a sick visit) Trial B: Walmart pharmacy customers will be included if they: - Have consented to receive text messages about their Walmart prescriptions - Have received a flu shot from Walmart in the past - Have been selected for study inclusion by Walmart

Key exclusion criteria

Trial A: - Has documentation of allergy or adverse event to influenza vaccination in medical records - Has documentation of already receiving their 2020 influenza vaccination prior to randomization in medical records - Has opted out of receiving text message appointment reminders - Has asked not to be contacted for research purposes - Has an appointment with someone other than their primary care physician - Has an appointment with someone other than a physician, resident, nurse practitioner, or physician assistant. Trial B: None

Vulnerable Populations

Children Form

Pregnant women (if the study procedures may affect the condition of the pregnant woman or fetus) Form

Fetuses and/or Neonates Form

Prisoners Form

Other

None of the above populations are included in the research study

The following documents are currently attached to this item:

There are no documents attached for this item.

Populations vulnerable to undue influence or coercion

Not applicable

Subject recruitment

Trial A: All eligible Penn Medicine and Geisinger patients with routine primary care appointments from September 1, 2020 to March 31, 2021 will be enrolled and randomly assigned to a study condition.

Trial B: All eligible Walmart pharmacy customers will be enrolled and randomly assigned to a study condition.

Will the recruitment plan propose to use any Penn media services (communications, marketing, etc.) for outreach via social media avenues (examples include: Facebook, Twitter, blogging, texting, etc.) or does the study team plan to directly use social media to recruit for the research?

No

The following documents are currently attached to this item:

There are no documents attached for this item.

Subject compensation*

Will subjects be financially compensated for their participation?

Yes

The following documents are currently attached to this item:

There are no documents attached for this item.

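### People are randomised one by one but texts go to phone numbers that need not be unique, so two participants on one number can be sent different arms

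*Protocol*

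**What the plan says.** **Unit of assignment.** Protocol, Method for Assigning Subjects to Groups, Trial A: "patients will be randomly assigned to experimental conditions using stratification that accounts for demographics (e.g., age), and recruitment site". The Design section adds provider role and unspecified other factors as possible strata. For Trial B, Subject recruitment says: "All eligible Walmart pharmacy customers will be enrolled and randomly assigned to a study condition". Neither phone number nor household is named as a unit or a stratum.

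**Unit of delivery.** Administration of Surveys and/or Process, Trial A: "Patient phone numbers from their Penn Medicine and Geisinger records will be shared with WayToHealth to deliver the text messages". Trial B messages go out through the pharmacy's own text platform.

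**Phone criteria.** Key inclusion criteria, Trial A: "Have a cell phone number recorded in a Penn Medicine or Geisinger database". Patients who opted out of text reminders are excluded. Trial B requires consent to prescription texts and lists no exclusions. Uniqueness of a number is not required in either trial.

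**Handling at number level.** Data Management mentions it for opt-out only: "Penn Medicine and Geisinger will also indicate which phone numbers have opted out of receiving text message reminders".

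**Timing.** Trial A: "Text messages will be sent up to four days prior to patients scheduled primary care appointments". In Trial B, Study duration says that messages may run over 4 days at the start of the flu season.

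**Analysis.** The Analysis Plan fixes an OLS regression of a binary vaccination indicator at the individual level. It does not mention shared numbers.

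**The concern.** The person is randomised and the phone is treated. When two participants have the same recorded number, as written each draws an arm separately. With many arms the two draws will nearly always differ, and either person may read both messages. The trial exists to rank messages against each other, so exposure to a second arm blurs the comparison of interest.

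Two consequences are possible. The contrasts between messages may be diluted. The outcomes of people on one number may also be correlated, for instance because they live together, and an individual-level regression ignores that.

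The unit of randomisation and eligibility are fixed in the protocol, so this is not a detail that would ordinarily be left to a SAP.

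**Working it through.** **1. The plan's own figure.** Accrual gives at least 4,000 participants per condition and at least 80% power for a 3% difference, read here as 3 percentage points. It gives neither a baseline rate nor an alpha. With a two-sided alpha of 0.05 (assumption), a comparison of two proportions with 4,000 per arm has this power:

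| Baseline (assumed) | Power for 3 points |
|---|---|
| 20% | 90.4% |
| 30% | 82.3% |
| 33% | 80.6% |
| 35% | 79.6% |
| 40% | 77.7% |

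The stated 80% is met up to a baseline of about 34%. This is context for the margin available and is not itself challenged here.

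**2. Chance that two sharers differ.** With *k* equally likely arms and separate draws it is 1 − 1/*k*. The protocol plans at least 40 conditions across the two trials. With *k* = 20 per trial (assumption) it is 1 − 1/20 = 0.95.

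**3. Dilution if responses average over the two messages.** Let *s* be the share of participants who share a number with one other participant (not given; assumed). Sharers with different arms are taken to lose half the contrast:

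contrast = 3 × (1 − 0.5 × *s* × 0.95)

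The power column uses 4,000 per arm, a 30% baseline and a two-sided alpha of 0.05.

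| *s* | Contrast (points) | Power |
|---|---|---|
| 0 | 3.00 | 82.3% |
| 5% | 3 × 0.97625 = 2.93 | 80.5% |
| 10% | 3 × 0.9525 = 2.86 | 78.6% |
| 20% | 3 × 0.905 = 2.715 | 74.5% |
| 30% | 3 × 0.8575 = 2.57 | 69.9% |

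The formula leaves out the small chance that the second message is the comparator itself. Counting that gives 3 × (1 − 0.5 × *s*), that is 2.925 points at 5% and 2.55 at 30%, so the picture does not change.

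**4. Additive effects.** Suppose each message adds its own effect whatever else is read. Under independent assignment the second message is then spread evenly over arms. It raises every arm's expected rate by the same amount and cancels from each contrast, which stays at 3.00 points. Dilution therefore needs overlap, saturation or averaging.

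**5. Correlation.** If one number gets one arm, a pair with correlation *r* has design effect 1 + *r*. With 10% of people in pairs and *r* = 0.3 (both assumed), the overall figure is 0.90 × 1 + 0.10 × 1.3 = 1.03. Under separate draws a sharer's partner is as likely to be in the comparator arm (1/20, lowering the variance of the difference) as in the same arm (1/20, raising it). The net effect on the standard error of a contrast is then close to nil.

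**6. Trial by trial.** In Trial A each person's texts are tied to their own appointment, and appointments run from September 1, 2020 to March 31, 2021. Both messages can act before the primary outcome only if the sharers' appointments are close, or for the person whose appointment comes later. Step 3 counts every discordant sharer as exposed, so for Trial A it is nearer an upper value under averaging. In Trial B the window is short and at the start of the season, so overlap is likelier.

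**The case against.** The strongest reply is that this is inferred from silence. The protocol never says that sharers are assigned independently. Its stratification is open to other factors, the pharmacy selects Trial B customers by rules not shown, and a duplicate check could sit in the randomisation specification or in either sender's platform. That is possible, but the text describes assignment by person, and the one step it does define at number level is opt-out.

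Sharing may also be rare. Trial A takes adults only, needs a cell number, and both sharers need an eligible visit. Each Trial B customer must have consented to texts and had an earlier flu shot there. Some messages carry a first name, which tells sharers whose message it is, though it does not stop the other person reading it. All of this limits the size, which is unknown.

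Several stronger readings are tempting and are not supported:

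- **Household members do receive competing arms and contrasts do shrink.** The documents do not show that any two participants share a number, and step 4 shows that shrinkage is conditional.
- **All Trial B texts arrive together.** Study duration says that messages may run over 4 days; timing varies by condition, and incentive messages can come later.
- **One person's text is mixed into another's replies.** The protocol says that replies are stored, but nothing shows such mixing.
- **The 80% power claim fails because of sharing.** At 5% sharing with averaging it still holds at a 30% baseline. Overlap is likeliest in Trial B, where 1,000,000 customers over even 40 arms is 25,000 per arm, far above 4,000. Dilution there would bias estimates without threatening power.
- **The individual-level standard errors are materially wrong.** Under separate draws step 5 gives little reason to think so. Clustering matters chiefly once the number is the unit of assignment.

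**Conclusion.** The point holds in a limited form. As written, two participants on one number can be sent different arms, and nothing in the eligibility criteria, the assignment method or the stated analysis deals with that. Contrasts between messages can be diluted, more plausibly in Trial B than in Trial A.

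The size cannot be fixed from the protocol. It is 2.93 to 2.57 points in place of 3.00 if 5% to 30% share a number, with 20 arms, pairs only, and responses averaging over the two messages. It is zero if effects add. This is a worthwhile improvement at low cost and not a flaw that undermines the trial.

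**What to change.** **If assignment can still be changed:** assign one condition per phone number in both trials. A later enrollee on a number inherits the first person's arm, and the strata are those of the first person enrolled. Cluster the OLS standard errors on the number.

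**Where assignment is complete:** this is probably the relevant part, since the document is dated 06/11/2021 and the Trial A appointment window closed on March 31, 2021.

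- Create a de-identified phone-number code and carry it into the analysis file before identifiers are stripped.
- Cluster the OLS standard errors on that code.
- Repeat the primary analysis without shared numbers. Define sharing from the source phone records and not from who was later enrolled, so that the exclusion does not depend on enrolment after randomisation.
- Report the share of participants on a shared number in each trial, which settles how much the point matters.

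**Cost:** a slightly larger variance under assignment by number (about 1.03 under the assumptions in step 5), slightly less exact stratification because sharers can fall in different age, site or provider strata, and one coded key from each of the two messaging platforms.
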